9.7 Data analysis

9.7.1 Definition of analysis sets

The safety analysis will be based on the SAS. The SAS will consist of all patients exposed to somapacitan during study period.

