9.5 Study sample size

The sample size calculations are performed for the primary endpoint (number of ADRs) and based on previous experience from the NordiNet[®] IOS⁶ where 2% of the paediatric patients with GHD experienced an ADR.

Table 9-4 shows the 95% confidence interval for an incidence of 2%, derived using the Wilson-score method.

Table 9-4 Sample size table (Wilson-score method)

Sample size	95% CI
100	(0.55, 7.00)
200	(0.78, 5.02)
300	(0.92, 4.29)
400	(1.02, 3.89)
500	(1.09, 3.64)

Based on the table above, a sample size of at least 400 patients (inclusive of both naïve and non-naïve paediatric patients) would be required to rule out the doubling of the incidence for ADRs. Therefore, the study is planned for the sample size of 400 patients.

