9.7.2.1 Analysis of primary endpoint

The primary endpoint is the number of ADRs from baseline to EOS. EOS will differ from patient to patient.

ADRs during the study period will be summarised by MedDRA SOC and PT. This summary is displayed with number and proportion of patients with at least one event, number of events, and event rate (events per 100 patient-years of exposure).

The combined data from NordiNet® IOS and ANSWER will be used as an external comparator for the occurrence of ADRs. The aggregated data from isolated GHD patients from the NordiNET/ANSWER study will be used for comparison of both baseline characteristics and ADR incidence rates. No statistical comparison is planned due to limitations in the observational nature of the data collection.

The correlation between ADR incidence and duration of somapacitan treatment will be analysed with Spearman rank-order correlation.

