9.9 Limitations of the research methods

Data collection for this study will reflect routine clinical practice rather than mandatory assessments at pre-specified time points. The study captures data in GloBE-Reg from many different regions and settings. As data collection will reflect national, regional, and local differences in routine clinical practice regarding diagnostics, laboratory analyses, and reporting of events, potential issues may arise due to the study design. These issues may result in heterogeneous reporting of specific outcomes and time points for collection. Therefore, it is important to take these differences into account during the interpretation of data.

AEs are collected into GloBE-Reg based on the answer to the below question:

"Since the last recorded clinical encounter in the GloBE-Reg registry, has the patient experienced any untoward medical occurrence (sign, symptom or disease)"

In addition, the physician is responsible for evaluating the seriousness and causality of the AEs.

The safety endpoints are therefore limited to the physician's evaluation of these questions, and due to the secondary collection of data this evaluation cannot be further investigated.

The data source for the study, GloBE-Reg, captures data from many different regions and settings. This leads to a potentially heterogeneous patient population and different local standard of care and data capture, e.g., local differences in diagnostics, laboratory analyses, and reporting of events. This could result in a risk of information bias.

There is a risk of selection bias in the study, affected by the willingness and/or ability of physicians and patients to participate in GloBE-Reg. In addition, any undiagnosed patients will not be able to participate, and the rate of underdiagnosis may vary between regions. This may lead to a selected patient population, which does not accurately reflect the underlying patient population and may result in limited data on certain subgroups.

The long-term follow-up is a strength of this non-interventional study, but also leads to a risk of loss to follow up.

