As with any observational study, there is potential for bias resulting from variable quality and completeness in the information on potential confounders. Age, gender, previous GH treatment and medical history are among the potential confounders, and information on these will be collected to the extent possible. However, potential unmeasured confounding factors cannot be ruled out.

The extent of missing information on IGF-I and other endpoints at EOS visit will be reported in the final report by descriptive summaries and graphical presentations of extent, and pattern of missing data. Missing data will not be imputed.

The proposed external comparators are finalised non-interventional studies and therefore have the same potential limitations as mentioned above. The comparability between the results of the studies and any limitations in the conclusions will therefore be thoroughly discussed in the final study report.

 Protocol
 Date:
 17 July 2024
 Novo Nordisk

 Study ID: NN8640-4787
 Version:
 3.0

 UTN: U1111-1294-5941
 Status:
 Final

 EU PAS No.: Pending
 Page:
 28 of 48

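### The ADR proportion is taken over all exposed patients, so those with no registry encounter after the first appear to count as ADR-free; report it also among patients with a later encounter

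*Protocol*

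**What the plan says.** - **Analysis set (section 9.7.1).** "The SAS will consist of all patients exposed to somapacitan during study period". Exposure is the only condition; no follow-up is required.
- **Capture of adverse events (section 9.9).** The registry asks: "Since the last recorded clinical encounter in the GloBE-Reg registry, has the patient experienced any untoward medical occurrence". The physician then judges seriousness and causality.
- **Primary summary (section 9.7.2.1).** ADRs are shown as "number and proportion of patients with at least one event, number of events, and event rate" per 100 patient-years of exposure. Section 9.7.2.2 treats AEs, SAEs, serious ADRs and medication errors the same way.
- **Missing data (section 9.9).** "Missing data will not be imputed". Loss to follow-up is named as a risk but not quantified.
- **Sample size (section 9.5).** The basis is an earlier study in which "2% of the paediatric patients with GHD experienced an ADR". At least 400 patients, it says, "would be required to rule out the doubling of the incidence for ADRs". Table 9-4 gives a Wilson interval of 1.02% to 3.89% for 2% of 400. No allowance is made for patients without follow-up.
- **Follow-up (sections 9.1, 9.1.2 and 9.7.2.2).** Individual follow-up is expected to exceed 5 years. Data come from usual clinic visits. A patient's observation normally ends at the last visit within the study.

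**The concern.** The capture question looks back from one registry encounter to the one before. A patient with only the first encounter has no on-study interval for it to cover. Under section 9.7.1 that patient is still in the denominator of the proportion with an ADR. With no imputation, nothing separates this patient from one who was followed and stayed free of ADRs.

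Such patients are foreseeable. Visits are not scheduled by the study, consent may be withdrawn at any time, and section 9.7.2.2 itself provides for physicians who stop supplying data. The safeguards in section 11.4 (alerts for blank fields, contact with centres, annual quality checks on 10% of cases) address incomplete records. They do not create an encounter that never took place.

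The quantity affected is the one that sizes the study. A diluted proportion could be read as excluding a doubling of 2% when the patients actually followed do not support that.

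**Working it through.** **Inputs.** From section 9.5: reference proportion 2%, planning N = 400, two-sided 95% Wilson interval. The limit to be excluded is 2 × 2% = 4%. The share f of exposed patients with no encounter after the first is not in the protocol; values of f below are assumptions, with a range of 0 to 20%.

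**Step 1: the plan's own figure.** The upper Wilson limit for proportion p and n patients is

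U = [p + z²/(2n) + z·√(p(1 − p)/n + z²/(4n²))] / (1 + z²/n), with z = 1.96.

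For p = 0.02 and n = 400:

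U = [0.02 + 0.004802 + 1.96 × √(0.000049 + 0.0000060025)] / 1.009604 = (0.024802 + 0.014536) / 1.009604 = 3.90%.

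Table 9-4 prints 3.89%. All five rows agree within 0.01.

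**Step 2: dilution.** If a proportion π of the followed patients have an ADR recorded and the rest cannot, the reported proportion is π(1 − f).

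| f (assumed) | Followed, of 400 | π = 2% reported as | π = 4% reported as | Upper limit, all 400 (π = 2%) | Upper limit, followed only (π = 2%) |
|---|---|---|---|---|---|
| 0 | 400 | 2.00% | 4.00% | 3.90% | 3.90% |
| 5% | 380 | 1.90% | 3.80% | 3.77% | 3.96% |
| 10% | 360 | 1.80% | 3.60% | 3.63% | 4.03% |
| 20% | 320 | 1.60% | 3.20% | 3.37% | 4.20% |

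The upper limits use expected, not whole, numbers of patients. At f = 10% the expected number with an ADR is 0.02 × 360 = 7.2. With a whole 7 of 360, the upper limit is 3.96%, still below 4%.

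**Step 3: room in the planned N.** There are two separate questions, on different premises.

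*(a) Eight patients with an ADR are observed, and only the denominator changes.* The observed proportion then rises as n falls.

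| Denominator | Proportion | Upper limit |
|---|---|---|
| 400 | 2.00% | 3.90% |
| 390 | 2.05% | 3.995% |
| 389 | 2.06% | 4.005% |
| 380 | 2.11% | 4.10% |
| 360 | 2.22% | 4.32% |

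Eleven patients without a later encounter (11/400 = 2.75%) are enough to lose the exclusion of 4%.

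*(b) The proportion among followed patients is held at 2%.* The upper limit is 3.999% at n = 369 and 4.003% at n = 368. So 369 evaluable patients are needed, and 400 enrolled tolerates f up to 31/400 = 7.75%.

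**Step 4: the rate.** A patient never seen again contributes almost no time if person-time stops at the last encounter, as the in-study definition in section 9.7.2.2 suggests. Events per 100 patient-years are then nearly unchanged. They would be diluted too if exposure were counted to the data cut or from a treatment start before consent.

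**The case against.** Several objections have force.

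- **The mechanism is partly inferred.** The protocol gives the wording of the question. It does not say that nothing can be recorded at a first encounter, or that patients without a later one are scored as event-free. Both follow from reading sections 9.7.1, 9.7.2.1 and 9.9 together. This stands, so the point is put as what appears to happen.
- **The size is unknown.** Follow-up is expected to exceed 5 years and continues after somapacitan is stopped. At f = 10%, 40 of 400 treated children would never be seen again. This stands: f may be small. Also, 400 is a minimum.
- **No formal decision rests on the proportion.** Section 9.7.2.1 plans no statistical comparison, and the external comparison uses incidence rates. The 4% criterion appears only in the sample-size section. This limits the consequence, but the proportion is still a reported primary result and the sole basis for N.
- **An all-exposed safety set is conventional, and restricting it selects patients.** If ADRs prompt return visits, the restricted proportion is too high. This stands and argues for showing both denominators.
- **This belongs in the SAP.** Only in part: the protocol itself fixes the set and the 400.

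A reader might also infer that the comparison with the earlier studies always favours somapacitan. The documents do not support that, because the denominator behind the 2% is not described and may carry the same dilution. Nor do they support a claim about the annual progress reports: the protocol does not say that those reports tabulate this proportion.

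**Conclusion.** The point holds as a downward bias, by the factor (1 − f), in the proportion of patients with at least one ADR and in the parallel proportions for the other count endpoints. It rests on reading the capture question as needing an earlier registry encounter. The direction is fixed for any f above zero; the size cannot be established from the protocol and may be small.

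It merits attention because the planned N leaves little room: 2.75% of 400 without a later encounter removes the exclusion of 4% when 8 ADR patients are observed, and about 7.8% does so when the proportion among followed patients is 2%.

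It does not show that the all-exposed set is wrong, that the rate comparison is biased, or that the final report will be materially misleading. It is a cheap improvement to the reporting of one statistic.

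**What to change.** Keep the all-exposed SAS. In sections 9.7.1 and 9.7.2.1 add that:

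1. the proportion of patients with at least one ADR is also reported, with its Wilson 95% interval, among exposed patients who have at least one GloBE-Reg encounter after the first;
2. the number of exposed patients with no such encounter is reported;
3. any statement about ruling out a doubling of the 2% rests on that evaluable denominator, with a note that the denominator behind the 2% may differ.

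The cost is a sentence or two in the protocol, one disposition row and one extra line in the ADR summary. No new data are needed. There are two downsides. The evaluable number may fall slightly below the number enrolled; if 400 evaluable patients were wanted, 400/(1 − f) would have to be enrolled, which is 422 at an assumed 5% and 445 at 10%. Restricting to patients who return can also select patients, which is why both figures should be shown side by side.

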9.7.2 Statistical methods

Data of at least 400 paediatric patients will be drawn from the registry (GloBE-Reg) and investigated for long-term safety of somapacitan.

9.7.2.1 Analysis of primary endpoint

The primary endpoint is the number of ADRs from baseline to EOS. EOS will differ from patient to patient.

ADRs during the study period will be summarised by MedDRA SOC and PT. This summary is displayed with number and proportion of patients with at least one event, number of events, and event rate (events per 100 patient-years of exposure).

The combined data from NordiNet® IOS and ANSWER will be used as an external comparator for the occurrence of ADRs. The aggregated data from isolated GHD patients from the NordiNET/ANSWER study will be used for comparison of both baseline characteristics and ADR incidence rates. No statistical comparison is planned due to limitations in the observational nature of the data collection.

The correlation between ADR incidence and duration of somapacitan treatment will be analysed with Spearman rank-order correlation.

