This registry-based study will only investigate paediatric patients from the GloBE-Reg who have GHD and have been treated with somapacitan.

Additional information on each of the safety concerns to be addressed by this PASS is provided below.

Long term safety

Novo Nordisk A/S has included 'long-term safety' as missing information in the RMP for paediatric GHD.

The paediatric pivotal trial NN8640-4263, included in the submission package, included safety information from subjects with up to one year (52 weeks) of somapacitan exposure (i.e., short term/intermediate term). No safety data for patients with >1 year (52 weeks) of somapacitan exposure were included. Therefore, 'long term safety' is classified as missing information in the RMP and is included as the primary objective in this PASS.

Neoplasms

GH is anabolic and mitogenic, and IGF-I is antiapoptotic. Both hormones can cause proliferation of normal and malignant cells. In general, hGH treatment increases the blood IGF-I levels, but data do not generally support a carcinogenic effect of treatment with GH and there is no established relationship between high blood IGF-I levels and the risk of a malignancy. 12-14

T2DM

Treatment with GH may decrease insulin sensitivity, particularly at higher doses in susceptible patients. Consequently, hyperglycaemia may occur in subjects with inadequate insulin secretory capacity. As a result, previously undiagnosed impaired glucose tolerance and overt T2DM may be unmasked during GH treatment.

Impaired insulin sensitivity is a hallmark of T2DM. This effect of GH has been partly linked to the lipolytic effects of GH resulting in increased plasma levels of free fatty acids, plasma glucose and insulin levels in the hours following injections of hGH. 15, 16

 Protocol
 Date:
 17 July 2024
 Novo Nordisk

 Study ID: NN8640-4787
 Version:
 3.0
 3.0
 Status:
 Final
 Final
 Final
 Final
 Page:
 16 of 48
 17 July 2024
 Novo Nordisk
 Nordisk
 16 of 48
 17 July 2024
 Novo Nordisk
 16 of 48
 17 July 2024
 Novo Nordisk
 17 July 2024
 Novo Nordisk
 18 of 48
 18 of

Medication error

When there are both daily and weekly GH products on the market, there is a risk that the once weekly product might be mistakenly (by the patient/caregiver) administered daily, which could lead to incorrect dose administration rate and overdose.

When patients are used to take their injection daily, there is a risk that this will continue.

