9.1 Study design

EU PAS No.: Pending

This is a non-interventional, multi-national, single-treatment arm, observational, registry-based study to investigate the long-term safety and clinical parameters of somapacitan in paediatric patients with GHD under routine clinical practice conditions. The study design is shown schematically in Figure 9-1.

Figure 9-1 Schematic diagram of the study design

Abbreviations: GHD = growth hormone deficiency, FPFV = first patient first visit, LPFV = last patient first visit, and LPLV = last patient last visit.

The study population will consist of at least 400 paediatric GHD patients from the GloBE-Reg registry treated with once-weekly somapacitan and fulfilling the eligibility criteria of the present study (see Sections 9.2.2 and 9.2.3). The total duration of the study is planned for 10 years consisting of a 5-year recruitment period in the registry followed by a follow-up period of at least 5 years. Individual patients will be followed up from inclusion into GloBE-Reg until last routine visit within the full study duration, i.e. individual follow-up time is expected to be above 5 years. Patient data are planned to be collected beyond the age of 18 years and irrespective of discontinuation of somapacitan. The main purpose of this study is to observe patients for long-term safety. The planned study duration is from Q4 2024 until Q4 2034.

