9.1.1 Endpoint(s)

The primary endpoint of this study is to report all ADRs from baseline (week 0) to EOS (up to 10 years) to investigate the long-term safety in paediatric patients with GHD under routine clinical practice conditions.

The secondary endpoints and clinical parameters are described in Section 9.3.

External comparators:

The combined data from NordiNet[®] IOS and ANSWER will be used as an external comparator for the occurrence of ADRs and neoplasms, and data from the GeNeSIS study will be the external comparator for incident T2DM.

• The NordiNet® and ANSWER studies evaluated the safety of GH treatment as frequency and incidence rates of SAEs and/or treatment-related AEs including incidence rates of neoplasms. Both studies evaluated the safety of real-world treatment with Norditropin® for

Protocol		Date:	17 July 2024 Novo Nordisk
Study ID: NN8640-4787	CONFIDENTIAL	Version:	3.0
UTN: U1111-1294-5941	CONFIDENTIAL	Status:	Final
EU PAS No.: Pending		Page:	19 of 48

the indications requiring GH therapy according to normal clinical practice and treating physicians' discretion, including several paediatric indications including GHD. 6-8

• The GeNeSIS diabetes study included 11,686 GH-treated patients of which, baseline diabetes prevalence was evaluated from a cohort of 8,568 patients (3,368 in the US) who were GH-naïve at study entry. Prevalence and incidence (by SIR) were compared with results from patients aged less than 20 years in the US SEARCH for Diabetes in Youth study. 9,10

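### The primary ADR summary pools all time from baseline, so it does not show reactions beyond the 52 weeks of exposure that define the study's safety gap

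*Protocol*

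**What the plan says.** Section 7 of the protocol, under long-term safety, explains why the study exists. The pivotal paediatric trial in the submission covered up to one year of exposure. It continues: "No safety data for patients with >1 year (52 weeks) of somapacitan exposure were included". The consequence follows directly: "Therefore, 'long term safety' is classified as missing information in the RMP and is included as the primary objective in this PASS". The gap is thus defined by exposure, with its boundary at 52 weeks.

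Section 9.1.1 sets the primary endpoint as to "report all ADRs from baseline (week 0) to EOS (up to 10 years) to investigate the long-term safety", and section 9.7.2.1 repeats it: "The primary endpoint is the number of ADRs from baseline to EOS. EOS will differ from patient to patient". By system organ class and preferred term, the display gives the number and proportion of patients with an event, the number of events, and a rate per 100 patient-years of exposure. One analysis involves time: "The correlation between ADR incidence and duration of somapacitan treatment will be analysed with Spearman rank-order correlation".

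Other relevant text:
- Section 9.7.1: "The SAS will consist of all patients exposed to somapacitan during study period". No minimum exposure is set.
- Section 9.1: "individual follow-up time is expected to be above 5 years". Data collection continues after somapacitan is stopped, so follow-up time is not exposure time.
- Section 9.7.2.2 defines an in-study period and an on-treatment period; the latter ends at treatment stop. The listed subgroups (sex, age, dose, country or region, Tanner stage) do not include time since start.
- Section 9.7.2.2 analyses AEs, SAEs, serious ADRs and medication errors in the same way as the primary endpoint. The growth parameters, by contrast, are estimated by length of follow-up and treatment duration.
- Annex 1, checklist item 5.3, answers No to whether exposure is categorised by time windows.

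**The concern.** The question behind the study is what happens after the first year on drug. The primary analysis answers a different one: what happens over all observed time, first year included. A pooled rate averages the two periods. If ADRs cluster early, it overstates the later risk; if they rise later, it understates it. In neither case does the reader see the change.

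At stake is whether the final report can speak directly to the period named in section 7. As the protocol stands, the report need not state an ADR rate beyond 52 weeks of exposure, nor how many patients or patient-years lie beyond that point.

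**Working it through.** **1. The plan's own figure.** Table 9-4 gives a Wilson 95% interval of (1.02, 3.89) for 2% at N = 400. With p = 0.02, n = 400, z = 1.96:
- centre = (p + z²/2n)/(1 + z²/n) = (0.02 + 0.004802)/1.009604 = 0.02457
- half-width = [z/(1 + z²/n)] × √(p(1−p)/n + z²/4n²) = 1.94136 × 0.007416 = 0.01440
- interval 1.02% to 3.90%, which reproduces the table within 0.01.

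This precision concerns a pooled proportion. No exposure duration is attached to the 2%, so the table says nothing about ADRs after 52 weeks.

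**2. Can the planned output tell early from late ADRs?** Take 8 of 400 patients (2%) with one ADR each, all 8 treated for more than a year. In case A every ADR falls in year 1; in case B every ADR falls later.
- Count: 8 in both. Proportion: 2.0% in both.
- Pooled rate: same events over the same person-time, so identical.
- Spearman: with one ADR value and one total duration per patient, both inputs are unchanged, so the coefficient is identical. In addition, 392 of 400 patients (98%) tie at zero ADRs.
- On-treatment restriction: all events are on treatment in both cases, so it does not separate them.

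**3. How large is the year-1 share?** The protocol gives no discontinuation rate. Assumptions: all patients start somapacitan at entry; follow-up F is uniform on 5–10 years; discontinuation is exponential at d per year, with λ = −ln(1−d); the year-1 ADR rate is R times the later rate.
- Year-1 exposure per patient: y = d/λ (1 if d = 0).
- Total per patient: T = (1/λ)[1 − (e^(−5λ) − e^(−10λ))/(5λ)] (7.5 if d = 0).
- Year-1 share of ADRs: R·y/(R·y + T − y). It exceeds one half when R > (T − y)/y.

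| d per year | T (years) | Share, R = 1 | Share, R = 5 | Share, R = 10 | R needed for a majority | Patient-years beyond year 1, N = 400 |
|---|---|---|---|---|---|---|
| 0% | 7.50 | 13% | 43% | 61% | 6.5 | 2,600 |
| 10% | 5.13 | 18% | 53% | 69% | 4.4 | 1,674 |
| 20% | 3.60 | 25% | 62% | 77% | 3.0 | 1,080 |
| 30% | 2.58 | 33% | 71% | 83% | 2.1 | 697 |

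**4. What a split would show.** For cases A and B at d = 10%, the pooled rate is 8/(400 × 5.13) = 8/2,052 = 0.39 per 100 patient-years in both. The rate beyond 52 weeks is 0 in A and 8/1,674 = 0.48 in B. At d = 20%, the pooled rate is 8/1,440 = 0.56 in both; the late rate is 0 or 8/1,080 = 0.74.

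If no late ADR were seen, the rule of three (upper 95% limit about 3/person-time) gives 0.12, 0.18, 0.28 and 0.43 per 100 patient-years for d = 0, 10, 20 and 30%.

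**The case against.** **The SAP may add the split.** Section 4.10 leaves detailed elaboration to the SAP, which is not at hand, and checklist item 5.3 does not forbid time windows there. That stands as far as table layouts go. But the protocol fixes the pooled summary, chooses a duration analysis that cannot date events, and gives a duration breakdown to growth parameters but not to safety counts. Naming a better analysis is therefore more than asking for omitted detail.

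**The plan does look at duration and exposure.** It does: there is the Spearman analysis, the rate uses patient-years of exposure, and an on-treatment period is defined. A reader might infer that a patient treated for months counts fully as long-term exposure. The documents do not support that: such a patient counts fully in the 400 and in the proportion, but adds only months to on-treatment person-time. What remains is that none of these separates early from late exposure.

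**Year 1 may be a small part.** This is fair. A reader might infer that first-year reactions will dominate, but at a constant rate they do not. For patients already on somapacitan at consent, some or all of year 1 precedes observation, since the on-treatment period is part of the in-study period, which starts at consent. That lowers the share further.

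**Two other readings go too far.** One is that no data beyond 52 weeks exist at all. Section 7 speaks only of the submission package, and titles in the reference list mention 2-year and 4-year results. The other is that the risk-management gap would be closed on first-year evidence. The protocol states no rule for closing it.

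**Conclusion.** The concern holds as a mismatch between the exposure boundary in section 7 and the pooled primary summary in section 9.7.2.1. A baseline-to-EOS count does not contradict the long-term objective, because it contains the late period, but it does not isolate that period. On the per-patient reading of the Spearman analysis, the planned ADR output can be identical for early and late reactions.

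The practical size is uncertain. Year 1 supplies about 13–33% of ADRs at a constant rate, and more than half only if the early rate exceeds the later one by a factor of about 2.1 (30% yearly discontinuation) to 6.5 (none). The discontinuation rates, rate ratios, uniform follow-up and start at entry are assumptions, not protocol figures. This is a worthwhile, inexpensive improvement, not an error that invalidates the plan.

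**What to change.** - **Section 9.7.2.1:** keep the pooled summary as the overall description. Add on-treatment ADR rates for cumulative somapacitan exposure up to 52 weeks and beyond 52 weeks. Patients already treated at consent enter at their attained exposure.
- **Same section:** report the number of patients and the patient-years beyond 1, 2 and 5 years of exposure, and refer to the beyond-52-week rate when concluding on long-term safety.
- **Section 9.3.1:** add the treatment stop date to the exposure variables. The list has the start date, initial dose and dose changes, while the on-treatment definition in section 9.7.2.2 already relies on a stop date.
- **Neoplasms and T2DM:** list events descriptively by time since start. Separate stratum rates would probably be too sparse in about 400 patients.

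The cost is one more split of a planned table, using dates that the on-treatment definition already needs. The downside is fewer events and wider intervals in the late stratum.

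### The ADR scales do not line up: sizing uses patients affected, the endpoint is a count, and the only person-time rate available for the external comparison counts every event

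*Protocol*

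**What the plan says.** Three places in the protocol describe ADRs on three scales.

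- **Sizing (section 9.5).** The starting point is NordiNet IOS, "where 2% of the paediatric patients with GHD experienced an ADR". The precision table (Table 9-4, five sample sizes from 100 to 500) "shows the 95% confidence interval for an incidence of 2%, derived using the Wilson-score method", and 400 patients "would be required to rule out the doubling of the incidence for ADRs". This is a proportion of patients.
- **Endpoint (section 9.7.2.1).** "The primary endpoint is the number of ADRs from baseline to EOS". This is a count of events.
- **Summary and external comparison (section 9.7.2.1).** ADRs are tabulated by SOC and PT with "number and proportion of patients with at least one event, number of events, and event rate (events per 100 patient-years of exposure"). The aggregated isolated-GHD data from NordiNet/ANSWER "will be used for comparison of both baseline characteristics and ADR incidence rates". The same paragraph adds: "No statistical comparison is planned due to limitations in the observational nature of the data collection".

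Section 9.9 gives the registry question through which AEs are captured: "Since the last recorded clinical encounter in the GloBE-Reg registry, has the patient experienced any untoward medical occurrence". Section 9.1 expects individual follow-up above 5 years, and section 9.1.1 allows up to 10. Section 9.7.2.2 analyses AEs, SAEs, serious ADRs and medication errors in the same way as the primary endpoint.

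**The concern.** A reader who looks in section 9.7.2.1 for the quantity behind ADR incidence rates finds one person-time measure, and it counts every event. If 2% of 400 patients have an ADR, about 8 patients supply all the events. The AE question covers the interval since the previous encounter and is asked over many years, so a recurrent reaction could be recorded more than once. The all-event rate could then be shaped by one or two patients or by one clinic's recording habit.

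The proportion of patients with at least one event does not fill the gap alone. It is unaffected by repeats, but it takes no account of follow-up, which differs between patients here and may differ between this study and the comparator. Neither planned measure is both robust to repeats and adjusted for time at risk.

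At stake is how the descriptive comparison with NordiNet/ANSWER is read. Section 7 says the comparison with historical data is there so that clinically relevant conclusions on long-term safety can be drawn.

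**Working it through.** **Inputs from the protocol:** 400 patients; 2% with an ADR; two-sided 95% Wilson interval (section 9.5); follow-up above 5 and up to 10 years (sections 9.1, 9.1.1). **Assumed:** mean follow-up of 5, 7.5 or 10 years; the repeat frequencies below. The documents give no repeat frequency.

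**1. The plan's own figure.** Wilson limits are [p + z²/2n ± z√(p(1−p)/n + z²/4n²)] / (1 + z²/n). With p = 0.02, n = 400, z = 1.96 this gives 1.02% to 3.90%, against 1.02 to 3.89 in Table 9-4. The other rows agree within 0.01. The upper limit first falls below 4% at n = 369, so 400 meets the stated aim on the patient-proportion scale.

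**2. Sensitivity of the all-event rate to one patient.** Expected affected patients: 400 × 0.02 = 8. Let 7 have one ADR record and one have r. The rate is 100 × (7 + r) / patient-years, and its ratio to the no-repeat case is (7 + r)/8, whatever the follow-up.

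| r | Events | Ratio | Per 100 PY at 5 / 7.5 / 10 years | Patients affected |
|---|---|---|---|---|
| 1 | 8 | 1.0 | 0.40 / 0.27 / 0.20 | 8 (2.0%) |
| 2 | 9 | 1.13 | 0.45 / 0.30 / 0.23 | 8 (2.0%) |
| 5 | 12 | 1.5 | 0.60 / 0.40 / 0.30 | 8 (2.0%) |
| 9 | 16 | 2.0 | 0.80 / 0.53 / 0.40 | 8 (2.0%) |

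**3. How often chance alone gives an apparent doubling.** Assume that the true rate equals the comparator's, that affected patients are binomial(400, 0.02), and that 15% of them are repeaters with r records, the rest having one. Expected events are 8 × [1 + 0.15(r − 1)]. Summing the binomial probabilities of all outcomes with more than twice that number:

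| r per repeater | Expected events | P(observed > 2 × expected) |
|---|---|---|
| 1 (first events only) | 8.0 | 0.3% |
| 2 | 9.2 | 0.7% |
| 3 | 10.4 | 1.6% |
| 5 | 12.8 | 3.2% |
| 9 | 17.6 | 5.4% |
| 24 | 35.6 | 12.0% |

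**4. What a first-ADR rate would show.** For 8 first events the exact Poisson limits are χ²(0.025; 16)/2 = 3.45 and χ²(0.975; 18)/2 = 15.76. At 3,000 patient-years (400 × 7.5, ignoring the small loss from censoring at the first ADR) that is 0.27 per 100 patient-years (0.12 to 0.53). The upper limit is 15.76/8 = 1.97 times the estimate, so 400 patients would still keep it below a doubling on this scale.

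**The case against.** The case against making much of this is strong in several respects.

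- **The proportion sits in the same table.** One patient with many records would appear as one patient and many events, usually under one PT, so the inflation would be visible. This stands.
- **The term is undefined rather than wrongly defined.** Section 9.5 uses incidence for the share of patients, and section 9.7.2.2 calculates incidence rates for yes/no outcomes. A reader might infer that the all-event rate is the quantity compared and the proportion is not; the protocol does not say so.
- **The doubling criterion is on the proportion.** A reader might infer that one patient can create or hide the doubling that the study was sized to exclude. Repeat records cannot move that criterion. Repeats in a somapacitan patient only raise the somapacitan event rate; for the comparison to read too low, the comparator would have to count repeats too, and the documents do not say how it counts.
- **No inference rests on the rate.** No statistical comparison is planned, and no interval is named for the ADR rate. Criticism of a too-narrow Poisson interval would be aimed at an analysis that is not in the protocol.
- **The mechanism is assumed.** Injection reactions are not mentioned, nothing says an ongoing reaction is re-entered at each visit, and section 11.4 describes annual checks of 10% of cases with focus on adverse events. Rules for counting recurrences may properly sit in the SAP, which is not shown.

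What these points leave untouched is the mismatch within the protocol between sizing, endpoint and comparison, and the lack of a measure that handles both repeats and follow-up time.

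**Conclusion.** The point holds as a mismatch of scales and a cheap improvement, not as a flaw in a test or decision rule. With about 8 affected patients expected, the only person-time ADR rate defined doubles if one of them has 9 records, with no change in patients affected. That arithmetic needs only the protocol's 2% and 400, plus the assumption that such a patient occurs. How likely a misleading rate is depends on repeat frequencies that the documents do not give: with 15% repeaters, chance doubling runs from 0.7% at 2 records each to 12% at 24, so at modest recurrence the problem is small. The consequence is limited to the stability and clarity of a descriptive comparison, with the proportion alongside as a partial safeguard.

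**What to change.** In section 9.7.2.1:

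1. Add the first-ADR incidence rate (patients with a first ADR per 100 patient-years at risk, time censored at the first ADR) with an exact 95% CI.
2. Use it for the external comparison where NordiNet/ANSWER reports a patient-level rate. Otherwise compare the metric that source does report (patient proportion or all-event rate), state which one is matched, and show the first-ADR rate alongside.
3. Keep the all-event rate as a supplement. If an interval is given for it, use a patient-level bootstrap or a negative binomial model.
4. Apply the same to SAEs and serious ADRs, which section 9.7.2.2 analyses in the same way.

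The cost is a few sentences and one extra table column. The downside is that the comparator may offer no first-event figure. In that case a first-ADR rate must not be set against an all-event one, which is why the matched metric has to be named.
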